5. STUDY ASSESSMENTS AND PROCEDURES

5.1. Study Flow Chart

Table displays hereafter a detailed study flow chart (with all assessments).

Table 1: Study Flowchart

	Study Treatment Period								EOS (within a week after last dose)
	D-28	D1	D8	D29	D57	D85	D113		
Time Window	± 3 days		± 2 days	± 2 days	± 4 days	± 4 days	± 4 days		± 2 days
Obtained Inform Consent	X								
Check of IN/EX Criteria	X	X							
Physical Examination	X	X	X	X	X	X	X		X
Body Weight (kg)	X	X	X	X	X	X	X		X
Height Measurement (cm)	X								
Medical History and Concomitant Medications	X								
Clostridium difficile (stool antigen and toxin), CMV, TB	X								
Vital signs	X	X	X	X	X	X	X		X
ECG (12 lead)	X	X			X		X		X
Randomization		X							
Blood Pregnancy test (WOCBP)	X	X		X	X	X	X		FU
Hematology + Biochemistry	X	X	X	X	X	X	X		X + FU
Coagulation and Troponin		X	X	X	X	X	X		
Serum collection for patients with loss of response to biologics (neutralizing antibody)			X						
Modified Mayo Score (pMMSS/MMSS)	X [†]	X	X	X	X	X	X		X
e-Diary data collection	X	X	X	X	X	X	X		
Fecal calprotectin		X			X		X		X
Sigmoidoscopy	X				X			X	(Conditional)
IBDDQ		X			X			X	
ABX464/placebo treatment dispensation		X		X	X	X			
Blood samples drug pK	X*	X [#]	X [#]			X [#]	X*		
Blood sample Cytokines	X	X	X	X			X		
Samples for miRNA (Biopsy RNA Later)	X				X			X	
Samples for miRNA (Blood PAXgene tube)		X	X	X	X			X	
Adverse Events recording	X	X	X	X	X	X	X		X
Dermatologist Consultation in case of skin effect									

* Applicable to all randomized / D1: 0.5, 1.5, 3 h post-dose or 1, 2, 4 h post-dose; D113: pre-dose, 1, 2, 4 h post-dose or pre dose, 0.5, 1.5, 3 h post-dose. #: pre-dose only. FU = biological follow-up 3 Weeks after Day 120 (Hematology, Biochemistry and B-HCG) / No specific study visit required. [†]: pMMSS is calculated once within a week prior to screening endoscopy and Modified Mayo Score is calculated following endoscopy.

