5.2.2. Baseline (First dosing day / Day 1)

- Randomization: The Investigator needs to check the inclusion/exclusion criteria (central read of the endoscopy and patient's symptom score from e-diary) with respect to the procedures performed at screening visit and if applicable proceed with the patient randomization. Treatment numbers will be allocated at randomization via the IWRS and dispensed to the patient;
- IBD Questionnaire (as the patient's first procedure);
- Physical examination and vital signs;
- Body weight;
- 12 leads ECG;
- Population Pharmacokinetics blood samples at either 0.5, 1.5, 3h (and 6 h and/or 10 h if possible) or at 1, 2, 4h (and 8 h and/or 12 h if possible);
- Hematology and Biochemistry including blood pregnancy test for all women of childbearing potential, coagulation parameters and troponin;
- Blood sample for miR-124 (PAXgene® tube) and cytokines determination;
- Serum collection for patients with loss of response to previous biologics (i.e. neutralizing antibodies);
- Fecal calprotectin dosage;
- Partial Modified Mayo Score;
- Review the patient e-Diary;
- Adverse Events reporting;
- Dispense study treatment to patient and instruct how to take them (First dosing at site);
- Schedule next patient visits.

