5.2.3. Day 8, Day 29, Day 85 Visits

- Physical examination and vital signs;
- Body weight;
- Hematology and Biochemistry including coagulation parameters and troponin;

- Blood pregnancy test for all women of childbearing potential (D29 and D85 only);
- Blood sample for miR-124 (PAXgene® tube) and cytokines determination at Day 8 and Day 29 only;
- Check treatment compliance and review the patient e-Diary;
- Partial Modified Mayo Score;
- Population Pharmacokinetics blood samples pre-dose;
- Adverse Events reporting;
- Dispense study treatment (Day 29 and Day 85 only);
- Schedule next patient visits.

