5.3.8. Hematology and biochemistry

For hematology and biochemistry central laboratory will be used (i.e. Eurofins). All lab dosages will be done centrally. Sampling kits and transportation information and devices will be provided by Eurofins. Due to the outbreak of the SARS Cov-2 pandemic, some patients may not attend the study site, therefore hematology and biochemistry measurements may be done locally to assess the safety.

Regarding the calprotectin measurement, the local lab might be asked to keep back-up samples at -80°C till the end of the study.

The results of fecal calprotectin levels will not be communicated to either the study Sponsor or the Investigational site during the study in order to avoid any possible bias related to disease evaluation.

Each laboratory value that is outside of the central laboratory normal range will be identified. The Investigator will be responsible for assessing the clinical significance of laboratory abnormalities. If the Investigator is uncertain about the clinical significance of a laboratory abnormality, he/she will consult with the Sponsor medical monitor.

The Investigator should follow any clinically significant laboratory abnormalities until resolution.

Table displays the clinical laboratory parameters that must be measured.

Table 2: Laboratory Tests

HEMATOLOGY	BIOCHEMISTRY	STOOLS
Hemoglobin	Sodium	Fecal calprotectin
Hematocrit	Potassium	
WBC	Chloride	
Neutrophils	Calcium	
Lymphocytes	Phosphate	
Monocytes	Glucose	
Eosinophils	BUN or urea	
Basophils	Creatinine	
Platelet count	AST	
Prothrombin time (From D1 to D113 only)	ALT	
Fibrinogen (From D1 to D113 only)	GLDH	
	Lipase	
	Alkaline phosphatase	
	gGT	
	Total bilirubin	
	Total protein	
	Albumin	
	LDH	
	CRP	
	Total cholesterol	
	HDL cholesterol	
	LDL cholesterol	
	Troponin I & T (From D1 to D113 only)	

At each biochemistry time point, a tube containing the remaining serum (at least 1 mL) should be kept and stored at -20°C for potential further liver function parameters such as soluble caspase-cleaved keratin 18 (M30 Elisa) and/or miRNA22 as a marker of early hepatotoxicity.

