7.2. Premature trial discontinuation

A patient can be withdrawn at any time from the study for the following reasons:

- Investigator's decision; patient that would experience a treatment failure during the study may be withdrawn at any time. S/he will have to be treated according to standard of care as soon as s/he is off from study treatment;
- An Adverse Event or an intercurrent condition that preclude continuation of treatment;
 - Specifically, an increase $\geq 3.0 \times$ ULN in liver transaminases (AST/SGOT and/or ALT/SGPT) or an increase $\geq 2.0 \times$ ULN in Alkaline phosphatase or in total bilirubin requires close observation with repeating liver enzymes and serum bilirubin tests two times weekly and clinical investigation to understand the etiology of this elevation. Frequency of retesting can decrease to once a month if the abnormality stabilizes after this initial two weeks of follow-up and if the patient is asymptomatic. Discontinuation of the study treatment should occur if:
 - ALT or AST $> 8 \times$ ULN
 - ALT or AST $> 5 \times$ ULN for more than 2 weeks
 - ALT or AST $> 3 \times$ ULN and total bilirubin $> 2 \times$ ULN or INR > 1.5
 - ALT or AST $> 3 \times$ ULN with appearance of fatigue, nausea, vomiting, right upper quadrant pain or tenderness, fever, rash, and/or eosinophilia ($> 5\%$).
- Worsening of the UC defined, from Week 8 onwards, as a 2-point increase in the pMMS, with pMMS ≥ 4 on 2 separate occasions 7 day-apart and confirmed by an endoscopy sub-score of 2 points or higher;
- Major protocol violation;
- Patient's decision;
- Withdrawal of consent;

A patient who prematurely exits the study will not be replaced.

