17.2. LABORATORY EVALUATIONS

Results from the central laboratory for hematology and biochemistry, including blood pregnancy tests will be included in the reporting of this study. A list of laboratory assessments to be included in the outputs is presented in Table F below.

The results of Fecal Calprotectin levels will not be communicated to the study Sponsor, Investigational Site or blinded biostatistical team during the study to avoid any possible bias related to disease evaluation. These results will be made available post DBL in the unblinded final analyses.

Presentations will use *Système International* (SI) Units.

Quantitative laboratory measurements reported as “< X”, i.e. below the lower limit of quantification (BLQ), or “> X”, i.e. above the upper limit of quantification (ULQ), will be converted to X for quantitative summaries, but will be presented as recorded, i.e. as “< X” or “> X” in the listings.

The following summaries will be provided for laboratory data:

- Actual and change from baseline by visit (for quantitative measurements)
- Shift from baseline according to laboratory approved normal ranges (Low, Normal, High) for quantitative measurements
- Incidence of clinically significant abnormalities
- Listing of patients meeting abnormal criteria

The following clinical laboratory parameters will be summarized using descriptive statistics (n, mean, SD,

Document: \\ieedc-vnasc01\BIOSdata\Abivax\ABX464\FZA92720\Biostatistics\Documentation\SAP\ABX464-103_SAP_V2.0_10MAY2021

Author: [REDACTED]

Version Number: 2.0
Version Date: 10May2021

Template No.: CS_TP_BS016 Revision 5

Reference: CS_WI_BS005

Effective Date: 01Apr2018

standard error of the mean [SEM], median, minimum and maximum.):

Table F Laboratory Tests

HEMATOLOGY	BIOCHEMISTRY	STOOLS
Basophils	Alanine Aminotransferase (SGPT)	Fecal Calprotectin
Basophils/100 Leukocytes	Albumin	
Eosinophils	Alkaline Phosphatase	
Eosinophils/100 Leukocytes	Aspartate Aminotransferase (SGOT)	
Erythrocyte Mean Corpuscular Hemoglobin Concentration	Bilirubin, Total	
Erythrocyte Mean Corpuscular Volume	Blood Urea Nitrogen	
Hematocrit	C Reactive Protein	
Hemoglobin	Calcium	
Lymphocytes	Chloride	
Lymphocytes/100 Leukocytes	Cholesterol, Total	
Monocytes	Creatinine	
Monocytes/100 Leukocytes	Creatinine Clearance (Est)	
Neutrophils	Gamma Glutamyl Transferase	
Neutrophils/100 Leukocytes	Glucose	
Platelets	Glutamate Dehydrogenase	
Red Blood Cells	HDL Cholesterol	
White Blood Cells	LDL Cholesterol	

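### SAP Table F omits troponin, prothrombin time and fibrinogen, which the protocol measures at six visits and promises to summarise, and SAP 3.3 does not declare the change

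*SAP*

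**What the plan says.** **Collection.** Protocol 5.3.8 introduces Table 2 as the laboratory tests that have to be measured. Under hematology it lists "Prothrombin time (From D1 to D113 only" and "Fibrinogen (From D1 to D113 only", and under biochemistry "Troponin I & T (From D1 to D113 only". The flow chart in protocol 5.1 has a row "Coagulation and Troponin" with six marks. The visit descriptions agree: "Hematology and Biochemistry including blood pregnancy test for all women of childbearing potential, coagulation parameters and troponin" at Day 1 (5.2.2), the same item at Days 57 and 113 (5.2.4), and "Hematology and Biochemistry including coagulation parameters and troponin" at Days 8, 29 and 85 (5.2.3).

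**Analysis promised in the protocol.** Protocol 9.3 and 9.3.1 commit to descriptive statistics for laboratory parameters at each scheduled assessment, to shift tables from baseline, and to counts of patients with an abnormal value for each parameter by group and dose. Protocol 2.4 makes the number of clinically significant laboratory abnormalities per treatment group a secondary endpoint.

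**Analysis planned in the SAP.** SAP 17.2 states: "A list of laboratory assessments to be included in the outputs is presented in Table F below". Table F contains no troponin, prothrombin time or fibrinogen. SAP 3.3, which lists departures from the protocol, covers ECG statistics, potentially clinically significant abnormalities, miRNA, cytokines, pharmacokinetics and some subgroups. It does not mention these tests.

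**INR.** One of the liver discontinuation criteria in protocol 7.2, repeated in the synopsis, includes "ULN or INR > 1.5". INR is named in neither protocol Table 2 nor SAP Table F.

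**The concern.** The trial is meant to choose a dose, and a stated secondary objective is the safety profile of each dose group against placebo. A dose-related drift in a laboratory value that stays below what an investigator calls clinically significant shows up only in by-dose summaries and shift tables. If the SAP is programmed from Table F, that view is lost for coagulation and troponin.

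Two features of the documents add some weight. SAP 3.3 drops descriptive statistics for ECG parameters and leaves only normal and abnormal categories, so troponin is the remaining numeric cardiac marker among the required tests. Protocol 1.2.5.1 names the liver as a main target organ in the animal studies and says a liver monitoring plan is in place, so prothrombin time is a natural test to tabulate.

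The silence of SAP 3.3 matters in its own right. A reader of the study report could not tell whether the tests were left out on purpose or by oversight.

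**Working it through.** **Step 1. Confirm the number of draws from the protocol's own figures.** Protocol 5.4, Table 3, gives a volume per draw and a total per patient.

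- Fibrinogen and prothrombin time: 6 visits x 4.5 mL = 27.0 mL. Stated total 27.0 mL.
- Troponin I and T: 6 visits x 3.5 mL = 21.0 mL. Stated total 21.0 mL.

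Both totals are reproduced, so six draws (Days 1, 8, 29, 57, 85 and 113) are consistent across the flow chart, the visit descriptions and the blood-volume table. The two sets of tubes come to 27.0 + 21.0 = 48.0 mL per patient. This only confirms the schedule; it does not measure harm, because the samples also serve the monitoring of individual patients.

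**Step 2. Compare the two lists item by item.** Synonyms were matched (phosphate with phosphorus, gGT with gamma glutamyl transferase, BUN or urea with blood urea nitrogen), and troponin I and T were counted as the single entry that Table 2 gives them.

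| | Hematology | Biochemistry | Stools | Total |
|---|---|---|---|---|
| Entries in protocol Table 2 | 11 | 23 | 1 | 35 |
| Of these, in SAP Table F | 9 | 22 | 1 | 32 |
| Missing from Table F | 2 (prothrombin time, fibrinogen) | 1 (troponin I and T) | 0 | 3 |

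Table F also adds items that Table 2 does not name: red blood cells, MCV, MCHC, estimated creatinine clearance and the differential percentages. INR is not among them. The three missing entries are exactly those that Table 2 restricts to Day 1 through Day 113. That looks more like a block left out than a scattered slip, but the documents give no reason.

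**Step 3. Size.** With full follow-up, 6 visits x 244 patients = 1,464 scheduled results per parameter, for four parameters (troponin I, troponin T, prothrombin time, fibrinogen). At 61 patients per arm this is 6 x 61 = 366 per parameter and arm. Both are ceilings: protocol 9.4 assumes 5% dropout before Week 8 and expects somewhat more because of the pandemic, and some visits will be missed.

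**Step 4. Which outputs hang on Table F.** SAP 17.2 ties two things to Table F by its wording: the list of assessments for the outputs, and the descriptive statistics. The bullets on shift from baseline, clinically significant abnormalities and listings refer to laboratory data in general. So the loss of descriptive summaries follows directly from the text. The loss of shift and abnormality tables is the likely reading, since Table F is said to list what goes into the outputs, but it is not certain.

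**The case against.** The best case for the SAP has four parts.

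- **Section 17.2 is broader than Table F.** It opens by saying that central-laboratory hematology and biochemistry results will be reported, and protocol Table 2 files all three tests under those headings. SAP 8 leaves the format and content of tables to templates that are not among the documents. This stands in part. A reader might infer that no summary, shift table, abnormality count or listing of any kind would exist for these tests. The text does not support that; section 17.2 is ambiguous beyond the descriptive summaries.
- **Important values are captured elsewhere.** Under protocol 8.4.1, abnormalities that the investigator judges clinically significant are recorded as adverse events, and these are tabulated by arm. A data safety monitoring board also reviews safety every two months. This stands, but it does not replace the summaries and shift tables that the protocol promises for values below that threshold.
- **The loss is descriptive only.** SAP 17 plans no statistical comparison of safety data unless otherwise specified, and the documents cite no troponin or coagulation signal; the adverse events of interest are headache and skin lesions. This stands and limits the weight of the point.
- **INR comes from prothrombin time.** A reader might infer that the INR criterion cannot be applied because INR is not a listed test. The documents do not support this. Prothrombin time, from which INR is calculated, is drawn at six visits, the visit descriptions ask for coagulation parameters in general, and protocol 7.2 also calls for clinical investigation of a liver-test elevation. Whether INR is in Table F, an end-of-study list, has no bearing on decisions for individual patients. What remains is that INR is not named.

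**Conclusion.** The point holds as an undeclared departure of the SAP from the protocol's safety reporting. Three required entries out of 35, covering four parameters at six visits, are missing from the list that governs the laboratory outputs. Read as written, their by-dose descriptive summaries would not be produced, and probably not their shift and abnormality tables. At most 1,464 results per parameter are affected, and clinically significant values would still appear as adverse events. The primary analysis, the power and the dose-testing sequence are unaffected. It is worth correcting because the data are already collected and the promise is explicit.

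The conclusion rests on two assumptions: that Table F means what SAP 17.2 says it means, and that the unseen output templates do not quietly include these tests. If they do, only the SAP text needs correcting.

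The INR matter is separate and minor. It is a naming gap between protocol 7.2 and the two laboratory lists, and no view is taken here on the criterion itself.

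**What to change.** - Add troponin I, troponin T, prothrombin time and fibrinogen to SAP Table F, and state that the shift and clinically significant abnormality tables cover them. Table 2 starts these tests at Day 1, so the Day 1 value serves as baseline under SAP 6.2.
- If the omission was intended, declare it in SAP 3.3 with the reason.
- Separately, reconcile protocol 7.2 with protocol Table 2 and SAP Table F on INR, for example by stating that INR is reported with prothrombin time. Confirm with the central laboratory that it is, because no section says so.

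The cost is a few more rows in existing table shells. No new sample or visit is needed for the four parameters.

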Premature trial discontinuation	
Patient's premature trial discontinuation could occur for the following reasons:
 
 ▪ Investigator's decision; patient that would experience a treatment failure during the study may be withdrawn at any time. S/he will have to be treated according to standard of care as soon as s/he is off from study treatment; ▪ An Adverse Event or an intercurrent condition that preclude continuation of treatment: 
 ○ Specifically, an increase \geq 3.0 x ULN in liver transaminases (AST/SGOT and/or ALT/SGPT) or an increase \geq 2.0 x ULN in Alkaline phosphatase or in total bilirubin requires close observation with repeating liver enzymes and serum bilirubin tests two times weekly and clinical investigation to understand the etiology of this elevation. Frequency of retesting can decrease to once a month if the abnormality stabilizes after this initial two weeks of follow-up and if the patient is asymptomatic. Discontinuation of the study treatment should occur if: 
 ▪ ALT or AST $>$ 8xULN ▪ ALT or AST $>$ 5xULN for more than 2 weeks ▪ ALT or AST $>$ 3xULN and total bilirubin $>$ 2xULN or INR $>$ 1.5 ▪ ALT or AST $>$ 3xULN with appearance of fatigue, nausea, vomiting, right upper quadrant pain or tenderness, fever, rash, and/or eosinophilia ($>$ 5%). 		

Study n°	ABX464-103	Clinical Phase	IIb		
	Type of Study	Safety, Efficacy, Dose-Ranging Study			
	
 ▪ Worsening of the UC defined, from Week 8 onwards, as a 2-point increase in the pMMS, with pMMS ≥ 4 on 2 separate occasions 7 day-apart and confirmed by an endoscopy sub-score of 2 points or higher; ▪ Major protocol violation; ▪ Patient's decision; ▪ Withdrawal of consent. 				
Patient Follow-up	
On Day 113 +/- 4 days, eligible patients willing to continue study treatment will be able to take part in an Open Label Extension study (ABX464-104). In this extension study, all patients will be dosed with ABX464 50mg QD. ABX464-104 maintenance study is a separate clinical study requiring health authorities and ethics committees' approvals.
				

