1.2.5. Preclinical data of ABX464

1.2.5.1. Non-clinical background information

The toxicity of ABX464 and ABX464-N-Glu was studied in a range of rodent and nonrodent species (rats, rabbits, dogs, cynomolgus and marmoset monkeys, and mini-pigs) with treatment durations ranging from 2-weeks to 6/9 months. These studies have demonstrated that ABX464 and ABX464-N-Glu are overall well tolerated. Vomiting and ptalism were the major clinical sign, and the main target organs of ABX464 toxicity were the gastro-intestinal tract and the liver. The adverse effects noted on these organs were essentially mild/moderate but showed reversibility during the recovery phases.

ABX464 was found to be non-genotoxic. Its main metabolite, the ABX464-N-Glu was not mutagenic as assessed by an Ames test, an in vitro and an in vivo micronucleus assay.

Reproductive toxicity was assessed from fertility to postnatal development, in five studies. In rabbits, the maternal NOAEL was considered to be █ mg/kg od. and the NOAEL for the embryo-fetal development less than █ mg/kg od. In rats, the maternal NOAEL and the NOAEL for pup development and survival is considered to be lower than █ mg/kg od. The F1 generation NOAEL is considered to be 40mg/kg od. in absence of adverse effect at this dose-level.

In minipigs the main adverse finding was █ observed at dose levels of █ mg/kg and above. The liver lesions observed in the single animal administered █ mg/kg od, were not considered adverse. Based on this observation, the NOAEL is █ mg/kg od.

No signs of hepatotoxicity have been observed in any of the patients treated with ABX464 in the previously conducted or on-going clinical trials. ABIVAX and its clinical experts consider that patients treated with ABX464 are not at increased risk of developing a drug-induced hepatotoxicity.

A specific liver function monitoring plan has been implemented in the current clinical study.

Regarding the other observations made from the pre-clinical toxicology program, please refer to the current version of the Investigator's Brochure.

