- Patients who are receiving immunosuppressants in the form of azathioprine, 6-mercaptopurine, or methotrexate needed to be on a stable dose for at least 4 Weeks prior to screening visit. Patients taking methotrexate also are advised to take folic acid 1 mg/day (or equivalent) supplementation if there is no contraindication;
- Patients on probiotics (e.g., Culturelle® [Lactobacillus GG, i-Health, Inc.], *Saccharomyces boulardii*) must be on stable doses for at least 2 Weeks prior to the screening visit;
- Patients on antidiarrheals (e.g., loperamide, diphenoxylate with atropine) must be on stable doses for at least 2 Weeks prior to the screening visit;
- Patients who have received tumor necrosis factor [TNF] inhibitors, vedolizumab or other biologics must have discontinued therapy at least 8 Weeks prior to the screening visit due to lack or insufficient efficacy or intolerance;
- Patients previously treated with cyclosporine, tacrolimus or JAK inhibitors must have discontinued therapy at least 4 Weeks prior to the screening visit due to lack or insufficient efficacy or intolerance;
- Patients previously treated with tube feeding, defined formula diets, or parenteral alimentation/nutrition must have discontinued treatment 3 Weeks before the screening visit and

must be able to take, orally, appropriate amount of food (calories) and liquids to maintain body weight;

- Patients with surveillance colonoscopy defined as per ECCO guidelines;
- Patients with the following hematological and biochemical laboratory parameters obtained at screening:
 - Hemoglobin > 9.0 g dL⁻¹;
 - Absolute neutrophil count \geq 750 mm⁻³;
 - Platelets \geq 100,000 mm⁻³;
 - Total serum creatinine \leq 1.3 x ULN (upper limit of normal);
 - Creatinine clearance $>$ 90 mL min⁻¹ by the Cockcroft-Gault equation within 60 days prior to baseline;
 - Total serum bilirubin $<$ 1.5 x ULN;
 - Alkaline phosphatase, AST (SGOT) and ALT (SGPT) $<$ 2 x ULN;
- Patients are able and willing to comply with study visits and procedures as per protocol;
- Patients should understand, sign and date the written voluntary informed consent form at the screening visit prior to any protocol-specific procedures are performed;
- Patients should be affiliated to a social security regimen (for French sites only);

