3.3. CHANGES TO ANALYSIS FROM PROTOCOL

The FAS population will include subjects who received at least one dose of study treatment, and who have baseline data for at least one efficacy variable.

Descriptive statistics for electrocardiogram (ECG) parameters will not be calculated as per protocol.

Individual parameter results will be kept on site, but only the number of patients with normal, abnormal - not clinically significant (NCS) and abnormal - clinically significant (CS) results will be reported.

Potentially Clinically Significant Abnormalities (PCSA) will not be considered due to data unavailability.

The Country and US vs Non-US subgroup analyses will not be performed because of the small number of subjects from some countries.

Analyses of miRNA-124 levels in blood and tissue will be analysed and reported separately by an independent vendor and will be excluded from the final outputs and analysis conducted by IQVIA.

Additionally, pharmacokinetic (PK) results will also be reported separately by an independent vendor, but external data may be made available to IQVIA Biostatistics and the subgroup 'Week 16 ABX464-NGlu AUC0-12 level above/below 7 000 h*ng/mL' will be included in subgroup analyses, if available.

The analysis of the following secondary endpoints will not be addressed in this SAP:

- Change relative to baseline in miRNA-124 expression
- Change relative to baseline in infiltrate/histopathology (Sigmoidal) using the RHI
- IL-6, TNF α , IL-1b, IL-10 plasma concentrations
- Serum concentration of ABX464 and N-Glucuronide ABX464

Document: \\ieedc-vnasc01\BIOSdata\Abivax\ABX464\FZA92720\Biostatistics\Documentation\SAP\ABX464-103_SAP_V2.0_10MAY2021

Author: [REDACTED]

Version Number:
Version Date:

2.0
10May2021

Template No.: CS_TP_BS016 Revision 5

Reference: CS_WI_BS005

Effective Date: 01Apr2018

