17.2.1. LABORATORY REFERENCE RANGES AND AGE CRITERIA

Quantitative laboratory measurements will be compared with the relevant laboratory reference ranges in SI units and categorized as:

- Low: Below the lower limit of the laboratory reference range.
- Normal: Within the laboratory reference range (upper and lower limit included).
- High: Above the upper limit of the laboratory reference range.

In addition to the high and low quantitative laboratory assignments (as identified by means of the laboratory reference ranges), abnormalities will be classified as not clinically significant or clinically

Document: \\ieedc-vnasc01\BIOSdata\Abivax\ABX464\FZA92720\Biostatistics\Documentation\SAP\ABX464-103_SAP_V2.0_10MAY2021

Author: [REDACTED]

Version Number:

2.0

Version Date:

10May2021

Template No.: CS_TP_BS016 Revision 5

Reference: CS_WI_BS005

Effective Date: 01Apr2018

significant.

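### No output in the SAP text counts liver-test elevations by arm at the protocol's own ULN multiples, and the Low/Normal/High shift puts 1.2 and 8.1xULN in one category

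*SAP*

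**What the plan says.** **Liver as a monitored organ.** Protocol 1.2.5.1 reports that in the toxicology studies "the main target organs of ABX464 toxicity were the gastro-intestinal tract and the liver", and adds that this trial has a liver monitoring plan.

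**Entry.** Protocol 4.2.1 requires "Alkaline phosphatase, AST (SGOT) and ALT (SGPT) $<$ 2 x ULN" and total bilirubin below 1.5xULN at screening.

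**Action levels.** Protocol 7.2 and the matching synopsis section work in multiples of ULN.
- Close observation starts at 3xULN for ALT or AST, and at 2xULN for ALP or total bilirubin.
- Treatment stops at "ALT or AST $> 8 \times$ ULN"; at "ALT or AST $>$ 5xULN for more than 2 weeks"; at ALT or AST above 3xULN with bilirubin above 2xULN or INR above 1.5; or at ALT or AST above 3xULN with certain symptoms or eosinophilia.

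**Planned laboratory outputs.** SAP 17.2 lists four:
- observed values and changes by visit, with mean, median, minimum and maximum, in SI units;
- the shift table, described as "Shift from baseline according to laboratory approved normal ranges (Low, Normal, High) for quantitative measurements";
- the incidence of abnormalities classed as clinically significant;
- a listing of patients with abnormal results.

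SAP 17.2.1 defines the top category as "High: Above the upper limit of the laboratory reference range", without further grades.

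**Unscheduled values.** SAP 6.3 leaves them out of by-visit summaries but lets them count towards best or worst values, with the shift table as its example.

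**The concern.** The protocol manages liver safety on a graded scale, and the SAP summarises it on a scale with one step above normal. The entry limits make this sharper, because some patients may already be on the top step at baseline. For them the shift table cannot show worsening, however large.

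At stake is the safety comparison of three doses with placebo, a secondary objective in Protocol 2.2. Someone weighing the doses would want to know how many patients per arm reached the levels at which the protocol requires observation or stopping, and whether that number rises with dose. They would also want to know whether anyone met the joint transaminase and bilirubin criterion. No table described in the SAP answers either question directly.

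**Working it through.** There is no stated figure to reproduce. The check applies the SAP's rule to values that the protocol allows, and then goes through the other outputs.

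**Step 1: the shift rule.** With x in multiples of ULN, SAP 17.2.1 gives High if x > 1, otherwise Normal (or Low). Entry allows x < 2 for ALT, AST and ALP.

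| Baseline (xULN) | Later value (xULN) | Shift cell | Ratio | Change (xULN) |
|---|---|---|---|---|
| 1.5 | 1.2 | High to High | 0.8 | -0.3 |
| 1.5 | 3.1 | High to High | 2.07 | +1.6 |
| 1.5 | 5.1 | High to High | 3.4 | +3.6 |
| 1.5 | 8.1 | High to High | 5.4 | +6.6 |
| 1.01 | 8.1 | High to High | 8.02 | +7.09 |
| 1.99 | 8.1 | High to High | 4.07 | +6.11 |
| 0.8 | 1.2 | Normal to High | 1.5 | +0.4 |
| 0.8 | 8.1 | Normal to High | 10.1 | +7.3 |

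The first four rows run from an improvement to a value above the protocol's highest transaminase level, and all fall in one cell. So do the last two rows.

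**Step 2: by-visit statistics.** With 61 patients in an arm, one patient rising from 1.5 to 8.1xULN moves the mean change by (8.1 - 1.5)/61 = 0.11xULN, which nobody would notice. The maximum would show the value if it fell at a scheduled visit. But it is one number per arm and visit, in SI units, and it does not say how many patients passed a level. Unscheduled results from the twice-weekly liver follow-up are excluded here. Where a retest carries the same visit number, SAP 6.3 uses only the last value, so a peak may be replaced by a lower repeat. Unscheduled peaks do reach worst-value outputs such as the shift table, where they become High.

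**Step 3: clinically significant abnormalities.** Protocol 5.3.8 leaves this judgement to the investigator, and 110 to 150 sites are planned. The count has no fixed threshold.

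**Step 4: listing.** It is by patient, not by arm, and SAP 17.2 gives no numeric laboratory criterion beyond the reference range. By contrast, SAP 17.4.1 sets numeric criteria for vital signs.

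**Step 5: the joint criterion.** It needs two parameters from the same patient, and every table in SAP 17.2 handles one parameter at a time. SAP Table F has neither prothrombin time nor INR, so that alternative limb has no summary.

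**Illustration (assumed counts; the documents give none).** Suppose 1 to 3 of 61 patients on one dose exceed 3xULN and none on placebo do. That is 1/61 = 1.6% to 3/61 = 4.9%, against 0%. If 10 more patients in each arm drift just above ULN, the High counts are 11 to 13 against 10. With no such drift they are 1 to 3 against 0, and the shift table loses little, provided those patients were normal at baseline. How much is hidden depends on how common mild elevations are.

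**The case against.** **Other outputs exist.** A reader might infer that the SAP summarises liver tests only as Low/Normal/High shifts, so that a severe rise disappears from the report. The documents do not support that. SAP 17.2 has three further outputs. In addition, laboratory abnormalities that the investigator judges clinically significant are recorded as adverse events (Protocol 8.4.1), graded by CTC-AE 5.0 (Protocol 8.6), and tabulated by maximum severity (SAP 17.1.1). A patient stopped under the liver rules for such an event would appear in SAP 17.1.3. So graded liver information by arm does exist. It rests, however, on the investigator recording an event, and a level that calls for observation rather than stopping need not produce one. It is not a count against fixed levels.

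**No departure from the protocol.** Protocol 9.3.1 asks for descriptive statistics and shift tables, and the laboratory endpoint in Protocol 2.4 is a number of clinically significant abnormalities. The SAP delivers these. The multiples in Protocol 7.2 are rules for managing individual patients, and nothing makes them analysis categories. This stands.

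**The PCSA sentence.** SAP 3.3 says "Potentially Clinically Significant Abnormalities (PCSA) will not be considered due to data unavailability". A reader might infer that a liver-threshold analysis was removed here, and without good reason, since central-laboratory values are available. The inference fails. The protocol leaves PCSA to the investigator's consideration and not to ULN multiples, the sentence follows the ECG text, and SAP 17.2 keeps the clinically significant classification for laboratory data.

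**Little liver signal so far.** Protocol 1.2.5.1 calls the toxicology findings essentially mild to moderate and reversible, and reports no sign of hepatotoxicity in treated patients. The events of interest are headache and skin lesions. This limits the urgency. It does not remove the reason to tabulate a risk that the trial monitors.

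**Templates.** SAP section 8 refers to separate table templates, which are not part of the documents. They could contain such a table, so the point concerns the SAP text.

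**Conclusion.** The point holds as a cheap improvement, not as an error. The Low/Normal/High shift is the only objective, range-based categorical summary of liver tests in SAP 17.2, and it treats everything above 1xULN alike. No output in the SAP text counts patients by arm at the Protocol 7.2 multiples or by the joint criterion.

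The mechanism follows from the two documents without assumption. Its practical size is not known. It depends on how many patients enter above ULN and how many drift mildly above it, and neither document gives these numbers. Two limits apply. Entry for ALT, AST and ALP is strictly below 2xULN, and the 8xULN level concerns ALT and AST alone; ALP and bilirubin have their own observation level of 2xULN.

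**What to change.** Keep the existing shift table, which is what the protocol asks for. Add to SAP 17.2, by treatment arm:

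1. Tables of baseline against worst post-baseline value in multiples of ULN, using the levels already in Protocol 7.2. For ALT and AST: up to 1, above 1 to below 3, 3 to 5, above 5 to 8, above 8. For ALP and total bilirubin: up to 1, above 1 to below 2, 2 or more. Include unscheduled values, as SAP 6.3 allows for shift tables.
2. A count of patients with ALT or AST above 3xULN together with total bilirubin above 2xULN, or INR above 1.5 where available. State whether the results must come from the same sample or may come from any post-baseline time.

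A worst-value table cannot show the two-week duration in the 5xULN stopping rule. If that is wanted, it needs a short listing.

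The cost is SAP wording and two or three extra tables from central-laboratory results and reference ranges that SAP 17.2 already uses. No clinical threshold changes and no new data are needed.
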